5.0 STUDY PROCEDURES AND ASSESSMENTS

5.1 Schedule of Events

Group 1 (Healthy Volunteers):

The initial healthy volunteer safety study will last a total of 4.5 weeks. Healthy volunteers will have the study device applied for 3 consecutive days (up to 72 hours), followed by weekly visits for 4 weeks of observation for tolerance, side effects, and adverse reactions. Weekly visits will occur every 7 ± 2 days after the Day 3 visit.

Assessment	Screening (via phone)	Baseline	tion: Day 0Study Device	3 ± 0 days Treatment:	$y 7 \pm 2 \text{ days}^4 \text{ Follow-Up}$:	Unscheduled Visit
Informed Consent		X				
Medical history	X					
Concomitant medications	X	X	X	X	X	X
OhioHealth Research Institute Clinic Visit (Research Only)		X				
Critical Limb Care Center (Riverside Methodist Hospital Wound Center) visit (research-only)			X	X	X	
Shaving of left posterior calf		X				
Photograph			X	\mathbf{x}^5	X	
Noxsano Bandage application			X			
SAR Questionnaire			X	X	X	

Group 2 (Wound Care Subjects):

The wound care subject treatment period will consist of twice per week study device applications to a specific ulceration for up to the first 4 weeks of treatment and then weekly re-application thereafter. When deemed permissible by the clinical judgment of the principal or sub-investigator or when 4 weeks is reached, re-application of the study device will change to weekly. This weekly re-application will occur until the wound is healed, or for up to 12 weeks (whichever occurs first). For subjects that do not exhibit any reduction in wound size at 2 months, application will stop and standard treatment protocols will be pursued.

At the conclusion of the treatment period (maximum of 3 months), subjects will be followed every 3 months for 12 consecutive months for observation of late side effects or adverse reactions (up to 3 months of active treatment, 12 months of follow-up observation, 15 months maximum).

IRB# 1331496 Page 24 Version 6.0

⁴ Day 10, 17, 24, and 31

⁵ Photograph and compensation are given on Day 3 only during Treatment Period

Assessment	Screening / Baseline	Day OInitial Study Device	ery 3 ± 2 days ⁶ Treatment:	$2 \text{ try } 7 \pm 2 \text{ days}^7 \text{ Treatment:}$	$imo \pm 14 days^8 Follow-Up$:	Unscheduled Visit
Informed Consent	X					
Routine medical history / physical exam	X					X
Concomitant medications	X	X	X	X	X	X
HgbA1c (subjects with diabetes)	X					
ABI (subjects with arterial insufficiency)	X					
Critical Limb Care Center visit (Riverside Methodist Hospital Wound Center)	X	X	X	X	X	X
Photograph (i.e., wound image)	X	X	X	X	X	X
Wound measurements	X	X	X	X	X	X
Percent granulation tissue	X	X	X	X	X	X
Noxsano Bandage application		X	X	X		
SAR Questionnaire		X	X	X	X	X

5.2 Concomitant Medications

A list of all prescription and over the counter medications, including topical treatments, will be recorded for all subjects at each visit.

Although subjects are excluded from Group 1 if they are on any prescription medications at the time of study initiation, due to the short duration of the procedure period (3 days), subjects who initiate prescription and/or over the counter medications during study participation will continue in the study.

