1.3.5 Group 1 (Healthy Volunteers) Rationale

Group 1 healthy volunteers are not dysfunctional in the generation of NO due to chronic wound healing, and therefore their endothelium will contain 'normal levels.' As such, use of the Bandage will represent an increase above physiologically normal levels in the endothelium of the healthy volunteers. In contrast, Group 2 subjects have wounds that are known to be dysregulated in NO. In this instance, the treatment returns their endothelium to physiologically normal levels of NO. Although the porcine study demonstrated efficacy, it could not indicate if irritation occurred as a side effect. As a result, a healthy volunteer group was included in this study to assess irritation from the use of the Bandage. As NO is a biologically-active species involved in a number of pathways in the endothelium, the manufacturer recommends a short 'acute exposure' of 72 hours. Longer-term overexposure could lead to artifacts as the body reacts to elevated levels of this biosignal.

The founders of Noxsano have worn devices for up to 72 hours with no apparent negative effects. The excess NO did appear to cause melanogenesis (skin darkening) and hyperemia (increased local blood flow). A period of 72 hours for Group 1 is therefore believed to be sufficient to determine if irritation occurs but short enough to avoid any potential artifacts from NO above physiological levels. Longer-term exposure to the Group 2 subject population is, in the opinion of the manufacturer, justified by the

IRB# 1331496 Page 16 Version 6.0

preclinical data from porcine studies. These studies demonstrate that long-term (weeks) NO exposure to chronic wounds leads to improved wound healing without any identifiable negative physiological effects (upon observation or histology).

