2.0 STUDY OBJECTIVES AND ENDPOINTS

2.1 Primary Objective

Group 1 (Safety): Healthy Volunteers. The initial phase of the study is designed to determine the safety of the study device in healthy volunteers without wounds. If there are no issues with tolerance, side effects, or adverse reactions in healthy volunteers, the second phase of the study will proceed with active wound care subjects.

For the purposes of this study, if two subjects experience an unacceptable adverse reaction warranting discontinuation of treatment in the opinion of the Investigators during the initial phase of the study, the study will be halted and the second phase (and the remainder of the initial phase, if applicable) will not be completed. Allergic reactions and infections at the bandage site will be considered unacceptable at any clinical severity; other adverse reactions will be deemed "unacceptable" by the Investigators on a case-by-case basis dependent upon clinical severity (App. A).

Group 2 (Efficacy): Wound Care Subjects. The second phase of the study is designed to determine the effectiveness of the study device in wound healing in subjects with active wounds (see Primary & Secondary Endpoints below).

[figure not shown]

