3.2 Subject Population and Sites

Group 1: Initial subjects will be limited to healthy volunteers with intact skin on their lower extremities. Five (5) white subjects and 5 black or African American subjects will be enrolled to evaluate skin differences. Group 1 (healthy volunteers without wounds) will have all follow-up completed and the results assessed before the investigators initiate prior to proceeding to Group 2 (wound care subjects).

Group 2: The subsequent wound care subject study will include 10 subjects from the patient population treated at the OhioHealth Riverside Methodist Hospital Critical Limb Care Center for lower extremity ulceration attributed to diabetes and/or arterial insufficiency.

[figure not shown]

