4.5 Exclusion Criteria

Group 1: Subjects will be excluded from the trial if **any** of the following criteria are met:

- 1. Subject is < 18 or ≥ 80 years of age.
- 2. Subject has a history of diabetes, arterial insufficiency, or osteomyelitis.
- 3. Subject has a known hypersensitivity to adhesives.
- 4. Subject is on any prescription medications, including contraceptives. Due to the short duration of the procedure period (3 days), subjects who initiate prescription medications during study participation will continue in the study.
- 5. Subject is pregnant, plans to become pregnant during the study period, or is breastfeeding.
- 6. Subject is non-English speaking or reading.
- 7. Subject is unable to give informed consent.

[figure not shown]
Group 2: Subjects will be excluded from the trial if **any** of the following criteria are met:

- 1. Subject is < 18 or ≥ 80 years of age.
- 2. The wound to be treated with the Noxsano bandage has a baseline wound surface area of ≥ 25 cm².
- 3. The wound to be treated with the Noxsano bandage is a plantar wound.
- 4. Subject with diabetes with an HgbA1c value of > 9.0, drawn within 3 months prior to study participation².
- 5. Subject with arterial insufficiency with an ABI value of < 0.40 or > 0.80, performed within 3 months prior to study participation³.
- 6. The wound to be treated with the Noxsano bandage has osteomyelitis contiguous with the treatment site.
- 7. Subject with peripherally-inserted central catheter (PICC) line antibiotic treatment within the previous 6 months.

IRB# 1331496 Page 22 Version 6.0

² Hemoglobin A1c is known to be significantly associated with wound healing rates, making it an important marker in the prediction of wound healing in diabetic patients [29]. A cutoff of 9.0% was chosen to exclude those with uncontrolled diabetes at highest risk for poor healing outcomes, as well as surgical complications including wound infections [30].

³ Patients with a normal-to-borderline ABI (> 0.80) are not characterized or diagnosed as having arterial insufficiency and are not referred to a vascular specialist; on the opposite end of the spectrum, those with severe arterial disease (< 0.40) typically proceed directly to hyperbaric treatment.

- 8. Subject requiring any type of amputation on the treatment limb within 3 months prior to study participation.
- 9. Subject with a known hypersensitivity to adhesives.
- 10. Subject is on active steroid therapy (does not include inhaled steroids).

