7.0 SAFETY REPORTING

7.1 Definitions

7.1.1 Adverse Event

An **adverse event** (AE) is any unfavorable or unintended event, physical or psychological, associated with a research study, which causes harm or injury to a research participant as a result of the participant's involvement in a research study. The event can include abnormal laboratory findings, symptoms, or disease associated with the research study. The event does not necessarily have to have a causal relationship with the research, any risk associated with the research, the research intervention, or the research assessments.

Adverse events may be the result of the interventions and interactions used in the research; the collection of identifiable private information in the research; an underlying disease, disorder, or condition of the subject; and/or other circumstances unrelated to the research or any underlying disease, disorder, or condition of the subject.

[figure not shown]
Subjects will be followed in terms of tolerance/side effects/adverse reactions:

- ♦ **Tolerance**: pruritus (itchy skin), dermatitis (dry skin), pain
- ♦ **Side effects**: erythema (red skin), edema (swollen skin), pressure ulcer (skin breakdown), melanogenesis (skin darkening), hyperemia (increased local blood flow)
- ♦ **Adverse reactions**: any systemic side effect, including (but not limited to) fever, nausea, vomiting, or hypotension (low blood pressure)

Group 1 healthy volunteers are not dysfunctional in the generation of NO due to chronic wound healing, and therefore their endothelium will contain 'normal levels.' As such, use of the Bandage will represent an increase above physiologically normal levels in the endothelium of the healthy volunteers. In contrast, Group 2 subjects have chronic wounds that are known to be dysregulated in NO. In this instance, the treatment returns their endothelium to physiologically normal levels of NO (see section 1.3.5).

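### Group 1 entry excludes every prescription medicine but not current over-the-counter products that can suppress the skin reactions the group is there to detect

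*Combined protocol and SAP*

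**What the plan says.** **Purpose.** Section 1.3.5 explains that "a healthy volunteer group was included in this study to assess irritation from the use of the Bandage". Section 3.2 sets the size: "Five (5) white subjects and 5 black or African American subjects will be enrolled to evaluate skin differences".

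**Entry.** The only Group 1 exclusion on medication is criterion 4 in section 4.5: "Subject is on any prescription medications, including contraceptives". No Group 1 criterion mentions over-the-counter or topical products.

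**During the study.** Section 5.2 requires that "A list of all prescription and over the counter medications, including topical treatments, will be recorded for all subjects at each visit". It also states, for Group 1, that "subjects who initiate prescription and/or over the counter medications during study participation will continue in the study", and gives the 3-day procedure period as the reason.

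**What is looked for.** Section 7.1.1 lists the tolerance signs as "pruritus (itchy skin), dermatitis (dry skin), pain", and places erythema and edema among the side effects.

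**How the result is used.** Under section 2.1 the study halts "if two subjects experience an unacceptable adverse reaction warranting discontinuation of treatment in the opinion of the Investigators" during the first phase. It adds that "Allergic reactions and infections at the bandage site will be considered unacceptable at any clinical severity"; other reactions are judged case by case on severity. The same section makes Group 2 conditional on there being no problems with tolerance, side effects or adverse reactions in the volunteers.

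**Analysis.** Section 9.0 does not say how recorded medication enters the reading of Group 1.

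**The concern.** Criterion 4 turns away a volunteer on a contraceptive but admits one who takes an antihistamine every day, uses an over-the-counter anti-inflammatory, or applies hydrocortisone to the calf. The documents do not name these products; they are examples of what the wording allows. They are used to relieve itch, redness and swelling, which are among the signs section 7.1.1 follows, and no reason is given for treating the two kinds of medicine differently.

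A reaction suppressed from the outset leaves no photograph, questionnaire answer or adverse event record. The medication list would show that the product was used, but not what would have happened without it. The error runs one way: a masked device reaction can only make Group 1 look safer. Group 1 is the step that decides whether wound patients are exposed for up to 3 months. It is also small: with five volunteers per racial group, one suppressed reaction moves that group's observed rate by 1/5 = 20 percentage points.

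**Working it through.** **1. What the plan already captures.**
- Section 7.2 requires treatment or action taken, and outcome, for every adverse event. Section 7.2.3 adds the date of resolution. So a reaction that appears and is then treated is identifiable as treated.
- Section 7.2.1 grades a reaction needing no specific intervention as mild, and one needing minimal or local intervention as moderate. Treating a visible reaction therefore does not lower its grade.
- Section 7.1.1 expects symptoms 24 to 72 hours after application. Section 5.7 keeps the device in place, unchanged, for up to 72 hours. Sections 5.3 and 5.8 require a photograph and the SAR questionnaire on Day 3. A product started after Day 3 cannot erase that record.

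What is left uncovered is a product already in use at entry: systemic use continuing through wear, or topical use on the calf shortly before application.

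**2. Whether use is recorded throughout.** The Group 1 schedule in section 5.1 marks concomitant medications at follow-up, and section 5.2 asks for them at each visit. The list of Group 1 follow-up evaluations in section 5.9 omits them. These need to be reconciled.

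**3. Effect on the two-subject rule.** The plan states no reaction rate or operating characteristic for this rule, so there is no figure of its own to reproduce. Inputs:
- n = 10 (section 3.2) and threshold 2 (section 2.1), from the documents.
- p = true rate of reactions that would count as unacceptable under section 2.1; assumed.
- u = share of volunteers using a masking product; assumed, and taken as unrelated to their risk of reacting.
- m = share of users' reactions hidden or made too mild to count; assumed.

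The observable rate is q = p(1 − u·m), and

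P(at least 2 of 10) = 1 − (1 − q)^10 − 10·q·(1 − q)^9.

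For p = 0.20:
- No masking, q = 0.20: 1 − 0.1074 − 0.2684 = 0.624.
- u = 0.1, m = 0.5, q = 0.20 × 0.95 = 0.19: 0.593.
- u = 0.2, m = 0.5, q = 0.20 × 0.90 = 0.18: 0.561.
- u = 0.3, m = 1, q = 0.20 × 0.70 = 0.14: 0.418.

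| Assumed p | No masking | 10% users, half masking | 20% users, half masking | 30% users, full masking |
|---|---|---|---|---|
| 0.10 | 26.4% | 24.5% | 22.5% | 15.2% |
| 0.20 | 62.4% | 59.3% | 56.1% | 41.8% |
| 0.30 | 85.1% | 82.6% | 79.8% | 65.4% |

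The no-masking column is the most that an entry restriction could restore. At p = 0.20 the loss is about 3, 6 and 21 points across the three scenarios.

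**The case against.** The strongest reply is that the plan already handles most of this. Medication is listed, treated reactions are recorded with outcome and date, and Day 3 is read before any later treatment could act. The covered site is also hard to reach with a topical product during wear. All of that stands, and it disposes of two stronger readings.

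- A reader might infer that letting volunteers continue after starting a medicine is itself a fault. It is not, because withdrawing them would lose safety data. Although observation runs four weeks beyond the 3-day reason given, those 3 days do cover the window in which onset is expected.
- A reader might infer that improvement after a newly started product would be counted as natural resolution. Nothing says so: section 9.0 defines no time-to-resolution analysis, and section 7.2 records the treatment.

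A further reply is that the binomial figures do not describe the whole decision. The halt rule counts only reactions judged unacceptable, not every itch or red patch. Allergic reactions and infections count at any severity, so mere softening would not remove them. Progress to Group 2 also depends on the broader condition in section 2.1 and on completed, assessed follow-up (section 3.2). This stands too: the table must be read with p as the rate of halt-qualifying reactions, and not as the chance that wound patients are exposed.

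None of this reaches the entry gap. A reaction that is fully suppressed triggers none of these safeguards, and softening can still matter for the reactions judged on severity.

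**Conclusion.** The concern holds as a minor and inexpensive improvement to Group 1 eligibility. Criterion 4 leaves out a class of products that can hide what the group was added to find, and any resulting error favours the device.

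The size is unknown. With few users and partial masking the loss in the chance of reaching two in 10 is about 3 to 6 points at an assumed 20% rate; it reaches about 21 points only with 30% users and complete masking. The reaction rate, the share of users and the strength of masking are all assumptions. The contents of Appendix A and of the addendum (section 10.0) were not available, so whether the questionnaire asks about self-treatment could not be checked.

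**What to change.** 1. **Section 4.5, Group 1 criterion 4:** extend it to current use of over-the-counter antihistamine, anti-inflammatory or corticosteroid products, whether systemic or topical on the calf. Check it from the medication list already scheduled at screening and baseline. The investigators should define what counts as current.
2. **Section 9.0:** list Group 1 SAR findings with and without volunteers who recorded such a product, showing its start date against the first sign of any reaction. The listing of all volunteers should remain the main one, because dropping those who took a product on account of a reaction would remove reactors.
3. **Sections 5.1, 5.2 and 5.9:** reconcile them on whether medications are recorded at Group 1 follow-up visits.

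None of this restricts the treatment of a reaction or removes a volunteer who starts a medicine. The cost is one clause, one listing from data the plan largely collects already, and a few more screen failures. The entry clause has no effect on volunteers already enrolled; the listing can still be produced for them.

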5.3 Photographs

Photographs of the study device application site and wounds (Group 2) will be taken using a digital camera, an FDA Class 1 510(k) exempt medical device. Digital photographs are routinely taken in the OhioHealth Riverside Methodist Hospital Critical Limb Care Center, therefore, their equipment will be utilized for the study.

Group 1(Healthy Volunteers): A photograph will be taken on Day 0 of the shaved area on the left posterior calf prior to study device placement. A photograph of the site where the study device was applied will also be taken on Day 3, following removal of the study device, and at each follow-up visit (Days 10, 17, 24, and 31). All photographs will be

IRB# 1331496 Page 25 Version 6.0

⁶ Weeks 1-4, 2 times per week study device changes or until change to weekly is permitted by investigator.

⁷ Weeks 5-12, weekly study device changes until wound has healed or 3 months is reached.

^{83, 6, 9,} and 12 months post-treatment

uploaded into the study electronic case report forms (eCRFs) by a member of the study staff.

Group 2 (Wound Care Subjects): Photographs of the wound with a conventional ruler in place will be obtained at baseline, Day 0 (Initial Device Application), treatment, and follow-up visits. Photographs will be taken by a wound care nurse and uploaded in the study eCRFs by a member of the study staff.

5.4 Wound Measurements

The standard measurement per the current protocol at the Center for Critical Limb Care is a vertical and horizontal measurement taken in centimeters using a conventional ruler. These measurements are used to calculate the wound area (cm²). All wound measurements for this study will be performed according to The OhioHealth Heart and Vascular Wound Care Center protocol to ensure consistency visit to visit. Current protocol involves trained nursing wound care staff obtaining photographic images with standard conventional ruler. Wound length, width, and surface area will be reported in the REDCap data collection tool. Sub-investigators will review the photographs to ensure in agreement with correct measurements.

5.5 Granulation Tissue

Percentage of granulation tissue present in the wound being treated with Noxsano bandage will be recorded in the REDCap data collection tool at each study visit.

5.6 Baseline Procedures

Group 1(Healthy Volunteers): If the subject meets inclusion/exclusion criteria and the informed consent is signed, a 4 x 4 cm segment of healthy, intact skin on the left posterior calf will be shaved by study staff. Study device application will occur within 1-3 days after the Baseline visit in the event that shaving causes irritation.

Group 2 (Wound Care Subjects): Baseline data will be collected, including a routine medical history and physical examination pertaining to study eligibility. The most recent documented baseline HgBa1c and/or ABI values will be collected from the subject's medical record. A baseline photograph and the standard wound measurement using a conventional ruler will be obtained as described in section 5.3. Baseline photographs will be taken with the conventional ruler in place. When possible subjects may proceed immediately to the initial study device application once baseline assessments have been completed.

5.7 Initial Study Device Application Visit

The device sizes available are small $(4 \times 4 \text{ cm})$, medium $(6 \times 6 \text{ cm})$, and large $(6 \times 8 \text{ cm})$, and are all 1-2 cm in thickness (1 cm) at the ends and 2 cm in the center, i.e., the location of the battery). The size used will depend on the size and shape of the wound to be treated (the device must cover the entire area of the wound) and could vary over time. Healthy volunteers will all receive the small $(4 \times 4 \text{ cm})$ device size.

IRB# 1331496 Page 26 Version 6.0

All subjects will be given a Noxsano Bandage Information Sheet (App. G), which will reiterate conversations from the Informed Consent process, including, but not limited to the following:

- ♦ "Troubleshooting" the Noxsano Bandage, including device malfunctions and frequently asked questions;
- ♦ Reporting safety issues, side effects, and adverse reactions.

Group 1 (Healthy Volunteers): A photograph will be taken on Day 0 of the shaved area where the device will be place prior to study device application. The study device will be applied by the Principal Investigator or delegated Sub-Investigator to the shaved area of skin on the left posterior calf. The study device will not be changed over the 3-day treatment period in order to complete an uninterrupted application of 3 total days (up to 72 hours). A photograph of the site where the study device was applied will also be taken on Day 3, following removal of the study device, and at each follow-up visit.

The SAR questionnaire will be administered by study staff immediately following application of the study device to assess tolerance, side effects, and/or adverse reactions (App. A). For the purposes of this study, if 2 subjects experience an unacceptable adverse reaction warranting discontinuation of treatment in the opinion of the Investigators during the initial phase of the study, the study will be halted and the second phase (and the remainder of the initial phase, if applicable) will not be completed.. Allergic reactions and infections at the device application site will be considered unacceptable at any clinical severity; other adverse reactions will be deemed "unacceptable" by the Investigators on a case-by-case basis dependent upon clinical severity (App. A).

Group 2 (Wound Care Subjects): The initial device application visit (Day 0) may be combined with the screening/baseline visit. Group 2 subjects will be limited to a maximum wound surface area of $< 25 \text{ cm}^2$, to allow for complete coverage with the largest device size of $6 \times 8 \text{ cm}$. Those with wounds $\geq 25 \text{ cm}^2$, comprising less than 5% of the wound care population, will be excluded. Conversely, we are not limiting minimum wound size, as some of the most complicated wounds are actually under 1 cm^2 .

The standard wound measurement in centimeters using a conventional ruler will be obtained according the The OhioHealth Heart and Vascular Wound Care Center standard protocol prior to the initial device application at Day 0. The standard measurement per the current protocol at the Center for Critical Limb Care will be implemented and a photograph with the conventional ruler in place will be taken.

The study device will be applied to the lower extremity wound site by a trained investigator or sub-investigator. Routine wound care techniques such as debridement will be performed in the usual standard fashion prior to application of the Noxsano Bandage. The SAR questionnaire will be administered by study staff immediately following application of the Noxsano Bandage to assess tolerance, side effects, and/or adverse reactions (App. A).

